## **1.0 Background and Significance**

Mechanical ventilation is life-saving technology but it can also inadvertently induce lung injury and increase morbidity and mortality. There currently is not an easy method of assessing the impact ventilator settings have on the degree of lung inflation. Computed tomography (CT), the gold standard for visually monitoring lung function, can provide detailed regional information of the lung (Figure 1). Unfortunately, it necessitates moving critically ill patients to a special diagnostic room and involves exposure to radiation.

A technique introduced in the 1980's, electrical impedance tomography (EIT) can non-invasively provide similar monitoring of lung function. However, while CT provides information on the air content, EIT monitors ventilation-related changes of lung volume and changes of EELV. Over the past several decades EIT has moved from the research lab to commercially available devices that are used at the bedside. One such system manufactured by Draeger Medical (Lubeck, Germany) is available in Europe and Canada but is not yet FDA approved for use in the United States. Draeger Medical has agreed to provide this system to the Adult Respiratory Care Department at the University of Michigan Health System for use in research. Our plan is to develop a series of research

protocols that build upon each other to provide us experience with the technology and insight on our practice of providing mechanical ventilation.

The EIT system consists of a 1.6-inch wide belt containing 16 electrodes, which is wrapped around the chest (Figure 2), generally at the level of the 4th - 6th rib. As an electrode pair emits a low alternating current (approximately 8 - 9 mA, depending on the frequency which can be set at 80 - 130 Hz), the resultant surface potential is measured by the remaining electrode pairs, and the impedance is determined. The adjacent electrode pair then emits a signal and the remaining pairs measure the potential. This sequence continues as the triggering of electrical emissions moves around the chest, via the belt, in a very rapid manner. One complete rotation creates voltage profiles at 16 positions of current emission, each consisting of 13 voltage measurements. The resultant 208 measurement values are reconstructed to provide one cross-sectional EIT image (Figure 3).

An exciting application for EIT is to monitor the regional and global distribution of tidal ventilation during positive pressure ventilation. Clinical studies have shown the value of EIT to quantify the effects of suctioning and ventilator disconnection, during placement of double-lumen endotracheal tubes, and to detect an incidental pneumothorax or pulmonary edema. Most importantly is the ability of EIT to assess lung recruitment and derecruitment as well as to assess for alveolar overdistension in an attempt to provide a lung protective ventilation strategy.

EIT has also been applied to study the effects of various devices used to provide noninvasive ventilation. Noninvasive ventilation (NIV) is a form of mechanical ventilation which does not involve placement of and attachment to an artificial airway. Rather the ventilator is attached to the subject via a face mask or other noninvasive interface. Pelosi evaluated three devices used to provide a form of NIV, continuous positive airway pressure (CPAP), that create airway pressure using different methods (high flow CPAP, low-flow CPAP and an ICU ventilator) and detected differences in breathing pattern, end-expiratory lung volume (EELV) and airway pressures between the devices. Andersson evaluated three CPAP systems using EIT in 14 healthy volunteers. They found different airway pressure profiles resulting in varying levels of EELV and noted that EELV increased more in ventral lung regions with increasing CPAP levels, independent of the system used, and a redistribution of tidal ventilation toward dorsal lung regions. EIT may prove useful to optimally adjust NPPV settings to improve ventilation and oxygenation.

Our plan is to perform a study similar to that described by Andersson as an initial project on the use of EIT.

## **2.0 Hypothesis**

We hypothesize that the distribution of ventilation and EELV in healthy adult subjects will not be different when NPPV is applied via different devices set to identical pressure settings. Also, when applying increasing NPPV pressures, the distribution of ventilation will shift from the ventral to dorsal regions and be similar between devices.

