## 5.0 Statistical Analysis

A two-way ANOVA will be the first step of analysis to determine the influence of the BiPAP systems on the NPPV. Regional distribution of tidal volume will be analyzed using four ventral to dorsal regions of interest (ROI) by EIT. The relative distribution of tidal volume between regions will be displayed as a percentage. Regional change in end-expiratory lung impedance (EELI) will be similarly expressed as a percent for each ROI. These parameters will be treated as functions of each individual step outlined in 4.6, with particular attention paid to the pressure support and PEEP. Values will be presented as mean  $\pm$  standard deviation and initial comparisons will be made using paired *t*-tests against baseline. Given the factorial design of experiment, if further analysis becomes warranted, a multivariate ANOVA will be utilized to determine the time, pressure, and total tidal volume relationship to relative distribution of tidal volume within the regions of interest. Potential confounding parameters such as patient size, weight, and health status will be screened in a similar manner.

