## 7.0 Benefits

There will be no direct benefit to the study subjects. This research will 1) provide an opportunity to learn the EIT system in a nonclinical application on healthy volunteers

before using it in a clinical protocol, and 2) allow comparison of NPPV systems that are routinely used clinically to hopefully show equivalence in important measures.

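### Section 2.0 predicts no difference between devices, but section 5.0 plans no interval, margin or other criterion that could support that prediction

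*Combined protocol and SAP*

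**What the plan says.** Section 2.0 makes two between-device predictions. The first is that "the distribution of ventilation and EELV in healthy adult subjects will not be different when NPPV is applied via different devices" at the same pressure settings. The second is that, as pressure rises, "the distribution of ventilation will shift from the ventral to dorsal regions and be similar between devices". Section 7.0 gives as the second benefit of the research that it will "allow comparison of NPPV systems that are routinely used clinically to hopefully show equivalence in important measures".

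The outcomes that carry these predictions are the secondary ones in 4.8: regional tidal variation and change in end-expiratory lung impedance (EELI). The primary outcome in 4.7 is Global Tidal Variation.

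Section 5.0 mentions the devices once: "A two-way ANOVA will be the first step of analysis to determine the influence of the BiPAP systems on the NPPV". For the other comparisons, "initial comparisons will be made using paired *t*-tests against baseline". Descriptively, "Values will be presented as mean" with standard deviation. A further step is conditional, introduced by the words "Given the factorial design of experiment, if further analysis becomes warranted". Should that condition be met, the plan is that "a multivariate ANOVA will be utilized to determine the time, pressure, and total tidal volume relationship to relative distribution of tidal volume". Neither document section gives a significance level, a confidence interval, an equivalence margin or any other criterion for the device comparison.

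**The concern.** A prediction of no difference needs a result that could bear it out: an interval narrow enough to rule out differences that matter, or a test against a stated margin. A difference test cannot do this. A non-significant device effect may mean that the devices behave alike, or that 20 subjects were too few to show how they differ, and the p-value does not separate the two.

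The stakes are practical. The two systems are in routine clinical use at the site. Section 1.0 describes earlier comparisons of CPAP devices that did find differences in end-expiratory lung volume, so a real difference is plausible. If the ANOVA is non-significant, the plan provides nothing that tells a reader how large a device difference remains compatible with the data.

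**Working it through.** **1. Each between-device statement set against each planned analysis**

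- *Two-way ANOVA.* It names the devices, but it is a difference test. Section 5.0 does not state its dependent variable, its two factors or a subject term. It could count against section 2.0 only if it is run on regional distribution and EELI with subject accounted for.
- *Paired t-tests.* They compare steps with baseline. They can address the ventral-to-dorsal shift, but they do not compare devices.
- *Conditional multivariate ANOVA.* It lists time, pressure and total tidal volume. If device is implied by the reference to a factorial design, it is still a difference test.
- *Mean and SD.* They show the size of a device difference but not its precision (step 4).

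No entry can support a claim of no difference or of a similar shift.

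**2. What one step can show (illustration)**

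The documents give no SD, alpha or sample size calculation, so there is no figure of the plan's own to reproduce. Inputs: n = 20 (section 3.1); both devices in every subject (4.2, 4.6.3). Assumed: two-sided alpha 0.05 and effects in units of SDd, the SD of the within-subject device difference. Paired t with 19 df.

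- Expected 95% CI half-width = c4 × t(0.975, 19) / √20 = 0.987 × 2.093 / 4.472 = 0.46 SDd.
- For a true difference of 0.5 SDd, the noncentrality is 0.5 × √20 = 2.236. The noncentral t gives power 0.565, so the result is non-significant with probability 0.435, about 44%.

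**3. Average over the three mask-on steps (4.6.1.2 to 4.6.1.4)**

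Assume the same true difference at each step and correlation r between the step-specific differences. The SD of the average is SDd × √((1 + 2r)/3).

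| r | SD of average (SDd) | Expected half-width (SDd) | P(non-significant) at 0.5 SDd |
|---|---|---|---|
| 0 | 0.577 | 0.267 | 0.044 |
| 0.3 | 0.730 | 0.337 | 0.173 |
| 0.5 | 0.816 | 0.377 | 0.262 |
| 0.7 | 0.894 | 0.413 | 0.340 |
| 0.9 | 0.966 | 0.446 | 0.406 |

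Averaging helps, and the range is 4% to 41%. How much it helps depends on a correlation that the documents do not give.

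**4. Why mean and SD per device are not enough**

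With equal per-device SD and within-subject correlation rho between devices, SDd = SD × √(2(1 − rho)). The one-step half-width is then 0.462 × √2 = 0.65 SD at rho = 0, and 0.462 × √0.2 = 0.21 SD at rho = 0.9. The same printed means and SDs fit both.

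**5. Why the estimate needs a period term**

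Order is set by coin toss (4.2), and the second device always follows a full first sequence (4.6.3). With a fair toss for each of 20 subjects, an exact 10/10 split has probability 184,756 / 1,048,576 = 0.176. The split is therefore unequal 82% of the time, and a period effect would then leak into an unadjusted device difference.

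**The case against.** The strongest reply is that this is a small familiarisation study. Section 7.0 puts learning the EIT system first, and the equivalence wording appears under Benefits, not in a decision rule. Predicting no difference and seeing whether the data contradict it is coherent, if weak. That stands as a reason for a light remedy, and none of the essential changes requires a margin or more subjects. It does not remove the mismatch, because section 2.0 states absence of a device difference as the hypothesis.

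A reader might infer that the plan will declare equivalence from a non-significant p-value. It states no such rule, and the point does not depend on one.

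A reader might also infer that the plan can at least refute the hypothesis. That goes too far, since section 5.0 does not say that the ANOVA is run on the relevant outcomes or with subject in the model.

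Nor do the documents show that the report must leave the precision unknown. A plan that does not mention intervals does not forbid them. If subject is modelled and the device means and the 1-df device F are reported, SE = |difference| / √F gives an interval for the step average. It does not give step-specific intervals. Nor does it give one for the similarity of the shift, because the device-by-step effect over three mask-on steps has (2 − 1) × (3 − 1) = 2 df. What is supported is that no such interval is planned.

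**Conclusion.** The point holds in a limited form. No planned result can support the between-device parts of section 2.0 or the hope expressed in 7.0. A significant ANOVA could count against them, on the condition given above. The ventral-to-dorsal shift itself is a claim of change that tests against baseline can address, so it is not affected.

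The textual finding rests on the documents alone. Its size is illustrative: 0.46 SDd expected half-width at one step, and non-significance at a true 0.5 SDd 44% of the time (4% to 41% for the three-step average with r from 0 to 0.9). These figures assume alpha 0.05 and 20 complete pairs. The value 0.5 SDd is a convenient benchmark, not a difference known to matter. A reader should not infer that 20 subjects are too few: the documents give neither an SD nor a relevant difference against which to judge that.

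**What to change.** Add to section 5.0:

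> The V-60 minus V-500 difference will be estimated with a 95% CI from a model with subject, period, device, step and device-by-step. It will be reported at each mask-on step and for the change between mask-on steps (the device-by-step contrast). The outcomes are regional distribution of tidal variation, EELI change, and Global Tidal Variation in impedance units or relative to baseline. A non-significant device effect will not be read as equivalence.

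The scale for Global Tidal Variation must be stated because the display described under Figure 4 fixes the global value at 100%, where a device difference has no meaning. The device-by-step contrast is what addresses similarity of the shift; separate intervals at each step do not.

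Restate the between-device parts of 2.0 and 7.0 as estimating the device difference. If an equivalence claim is still wanted, then before any data are analysed name the outcome, the step or contrast, and a margin in outcome units justified by what difference matters. Claim equivalence only if the 90% CI lies inside that margin.

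Cost: wording in three sections and intervals from data already collected, with no extra subjects or measurements. The period term uses one degree of freedom. The intervals are many: 10 measures (4 regional tidal variation, 4 regional and 1 global EELI, 1 Global Tidal Variation) at 3 steps give 30, and two successive changes per measure add 20. Of 50 unadjusted intervals, 50 × 0.05 = 2.5 would be expected to exclude zero if the devices were identical, so they should be read as estimates. The four regional percentages sum to 100%, so one of them is redundant. The sponsor may also find that an equivalence claim is not available.

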## **3.0 Subject Selection and Enrollment**

3.1 Subjects: Twenty adult healthy volunteers will be recruited for this study. They will be solicited from within the University of Michigan Health System (e.g. students, staff, and employees). No financial incentive will be provided.

3.2 Inclusion Criteria:

3.2.1 Age 18 years or older

3.3 Exclusion Criteria:

3.3.1 Use of a cardiac pacemaker, an implantable cardioverter-defibrillator (ICD) or any other active implants [electrical current may interfere with EIT signal]

## **4.0 Study Procedures**

4.1 Written informed consent will be obtained on all subjects prior to enrollment in the study and before any research procedures are performed. Subjects can withdraw from the study at any time.

4.2 Subjects will undergo testing by applying NPPV via 2 different BiPAP devices that are currently used in standard of care for patients at the University of Michigan Health System. The decision of which device to begin with will be determined by random allocation of a coin toss.

4.3 BiPAP Systems:

4.3.1 The Resironics V-60 (Phillips, Carlsbad CA) device is continuous high flow, blower type of generator.

4.3.2 The Drager V-500 (Drager Medical, Lubeck, Germany) is our primary critical care ventilator that has a specific NPPV mode.

- 4.4 EIT System: The Drager PulmoVista 500 EIT system (Drager Medical, Lubeck, Germany) consists of an electrode belt connected to the EIT monitor. Before using the system it will be reviewed and approved for use by our Biomedical Department.
- 4.5 Subjects will be placed in the supine position. This position will be maintained for the entire procedure. An electrode belt will be placed on the subject at the 5th intercostal space and connected to the EIT monitor. Prior to initiating a study session, the EIT system will be calibrated per manufacturer's instruction.
- 4.6 Each study device will be applied in the following manner:
  - 4.6.1 Four steps (series of device setting changes) will be applied, as such:
    - 4.6.1.1 A baseline will be established breathing without the NPPV mask attached
    - 4.6.1.2 Following mask attachment, a pressure support of 0 cm H2O and PEEP of 5 cm H2O will be applied, then
    - 4.6.1.3 A pressure support of 5 cm H2O and PEEP of 5 cm H2O, then
    - 4.6.1.4 A pressure support of 5 cm H2O and PEEP of 10 cm H2O.
  - 4.6.2 Each step will consist of a 5-minute stabilization period, and then readings will be taken over the next two minutes before proceeding to the next step.
  - 4.6.3 Following all four steps with the initial device, the second device will be applied and steps 1-4 repeated.
- 4.7 Primary Outcomes: Global Tidal Variation (see figures 4-6)
- 4.8 Secondary Outcomes:
  - 4.8.1 Regional Tidal Variations
  - 4.8.2 Global and Regional changes in End-Expiratory Lung Impedance (EELI)
- 4.9 Exploratory Outcomes:
  - 4.9.1 A pneumotachometer (NM3 monitor, Phillips Healthcare, Andover MA), will be placed between the mask and inspiratory hose and the following measurements obtained: respiratory rate, tidal volume, peak inspiratory

pressure, PEEP. A pulse oximeter (RAD8, Masimo, Irvine CA) will provide SpO2 and heart rate.

- 4.9.2 Change in regional and global distribution in subjects with a BMI less than or greater than 25 kg/m^2
- 4.9.3 Change in global and regional distribution for subjects at 0 degrees, 45 degrees, and 90 degrees' body positions.

4.10 In addition to device testing, baseline demographics such as age and gender will be recorded for each subject.

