## 6.0 Risks

The total procedure should be completed within 90-120 minutes. There is minimal risk or discomfort to the subject. The electrode belt will not be applied long enough for any chafing or skin breakdown to occur. Although hyperventilation (i.e. lightheadedness, tingling in the hands) may occur as airway pressure is applied, the subject will be monitored continuously and the pressures used are relatively low compared to those used clinically or at home for sleep apnea.

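### Starting device is set by an unrestricted coin toss and no period term is planned, so an unequal split of orders would let part of any period effect into the device comparison

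*Combined protocol and SAP*

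**What the plan says.** Section 3.1 gives the sample size: "Twenty adult healthy volunteers will be recruited for this study". Section 4.2 describes the comparison, "Subjects will undergo testing by applying NPPV via 2 different BiPAP devices", and the allocation of order: "The decision of which device to begin with will be determined by random allocation of a coin toss". Section 4.6.3 makes it a two-period crossover: "Following all four steps with the initial device, the second device will be applied and steps 1-4 repeated". The four steps start with a reading off the mask, so each device run has its own baseline.

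Section 5.0 begins the analysis as follows: "A two-way ANOVA will be the first step of analysis to determine the influence of the BiPAP systems on the NPPV". It adds paired t-tests against baseline. Time appears only in a further analysis, to be done if warranted, in which "a multivariate ANOVA will be utilized to determine the time, pressure, and total tidal volume relationship to relative distribution of tidal volume". There it is not defined as first or second device run.

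The document describes no blocking, target split, prepared list or concealment of order, and no period or sequence term.

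**The concern.** In a two-period crossover, anything that changes between the first and second run (time lying supine, habituation to the mask, signal drift) acts with opposite sign in the two orders. It cancels from a simple device difference only if the two orders are equally frequent. If they are not, a period term in the model is needed to remove it. The plan provides neither.

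A period effect is plausible, though the document gives no size for one. By section 4.6.2 each step takes 5 + 2 = 7 minutes, so the second run starts at least 4 × 7 = 28 minutes after the first. Section 4.6 states no washout other than the repeated off-mask step.

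The stake is the main claim. Section 2.0 hypothesises that the devices do not differ, and section 7.0 hopes to show equivalence. A shift due to order could create an apparent device difference or hide a real one, and with 20 subjects there is little room to absorb it.

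**Working it through.** **Inputs.** N = 20 (section 3.1). Two devices, hence two orders (sections 4.2 and 4.6.3). Order by coin toss (section 4.2). Assumed: a fair coin, tossed once per subject. The document gives no alpha, power, standard deviation, margin or intended split, so there is no planned figure to reproduce.

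**1. How uneven the split is likely to be.** The number starting on one device is Binomial(20, 0.5).

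- P(10:10) = C(20,10)/2^20 = 184,756/1,048,576 = 17.6%.
- Two-sided tails, 2·P(X ≥ r): 12:8 or worse 50.3%; 13:7 or worse 26.3%; 14:6 or worse 11.5%; 15:5 or worse 4.1%.

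**2. Leakage without a period term.** Let π be the change from first to second run. The within-subject device difference is shifted by +π in one order and −π in the other, so its mean carries π·(n1 − n2)/N.

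- 12:8: 4/20 = 20%.
- 13:7: 6/20 = 30%.
- 14:6: 8/20 = 40%.
- Over all splits the mean is zero and the root mean square is √(1/20) = 22%.

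**3. Precision with a period term.** The variance of the adjusted device contrast is proportional to 1/n1 + 1/n2. Relative to 10:10:

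| Split | Variance ratio | SE increase | Effective N = 4·n1·n2/20 |
|---|---|---|---|
| 11:9 | 1.010 | 0.5% | 19.8 |
| 12:8 | 1.042 | 2.1% | 19.2 |
| 13:7 | 1.099 | 4.8% | 18.2 |
| 14:6 | 1.190 | 9.1% | 16.8 |
| 15:5 | 1.333 | 15.5% | 15.0 |

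Averaged over all splits, variance rises by 6% and the standard error by about 3%. Average effective N is 19.0.

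**4. Calibration of the test.** This was simulated with an unadjusted paired t-test, N = 20, no true device difference, and π assumed between 0 and 2 standard deviations of the within-pair difference.

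- Coin toss per subject: type I error is 5.0% to 5.2% over the whole range.
- Coin toss, given a realised 14:6 split and π = 0.5 SD: about 10%.
- Fixed 10:10 list without a period term: 2.9% at π = 0.5 SD and 0.6% at π = 1 SD. The period effect cancels from the mean but still inflates the estimated variance, so the test is conservative.

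**5. After the change.** A permuted 10:10 list gives 10:10 at allocation with certainty, zero leakage in step 2 and a variance ratio of 1.00 in step 3, at the same N. Section 4.1 allows withdrawal: "Subjects can withdraw from the study at any time". Two random withdrawals leave 9:9 with probability 100/190 = 52.6% and 10:8 otherwise. If a single list of 20 were not concealed, the number of final allocations that could be known in advance averages 10/11 + 10/11 = 1.8.

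**The case against.** The strongest reply is that a fair toss for each subject is proper randomisation. Over repeated allocations it adds no bias, and the unadjusted test keeps its 5% level. That stands. A reader might infer from the leakage figures that the plan has a biased comparison or an inflated error rate; step 4 shows that it does not. What remains is conditional: the sponsor runs one trial and must interpret the split it gets.

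Second, a period term alone removes the leakage, after which imbalance costs little. In 74% of trials (100 − 26.3) the split is 12:8 or better, costing at most 2.1% in standard error. This also stands and limits the gain from the list itself. But the plan contains no such term.

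Third, each run has its own off-mask baseline, so values referenced to it could absorb additive drift or the effect of time supine. This stands in part. Section 5.0 does not say that the device ANOVA uses baseline-referenced values, and habituation to the mask arises after the baseline reading.

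Two further stronger readings should be set aside. A reader might take 10:10 to settle every order problem. It balances period effects and carry-over that is equal for both devices, but not carry-over that differs between them. A reader might also take section 4.2 to mean one toss for the whole study, which would put all 20 subjects in one order and fully confound device with period. The wording does not exclude this, but nothing in the document supports it, and a toss per subject is the natural reading.

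**Conclusion.** The point holds as a cheap improvement, of low to moderate priority; it is not a flaw that invalidates the comparison. Unequal orders are likely (82.4% of trials are not exactly 10:10, and half are 12:8 or worse). As section 5.0 stands, 30% or 40% of any period effect would enter the device difference at 13:7 or 14:6. With a period term the cost falls to about 3% in standard error on average, and 9.1% at 14:6.

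The split probabilities rest on a fair coin tossed per subject and on all 20 subjects completing. The leakage figures are shares of a period effect whose size the document does not give, so no absolute bias can be stated. The list and the period term do different work: the term removes the leakage at any split, and the list recovers the precision. Neither makes the other redundant, because a balanced list analysed without the term makes the test conservative. In a study that hopes to find no difference between devices, that is an unhelpful direction.

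**What to change.** In section 4.2, replace the coin toss with a pre-generated, randomly permuted list of 20 giving 10 subjects V-60 first and 10 V-500 first. It should be held by someone who does not run the sessions and opened one subject at a time. State that a withdrawn subject is replaced in the same order slot. In section 5.0, add period (first or second device run) to the within-subject device model, and say whether the modelled values are referenced to each run's own baseline.

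The cost is a short protocol change and a list made once. The planned sample and the session do not change, apart from replacing any withdrawals; section 6.0 already says "The total procedure should be completed within 90-120 minutes", and a single session of that length makes many withdrawals unlikely. The period term uses one degree of freedom. The downside is that the last few allocations are more predictable, which concealment limits and which matters little because every subject receives both devices. Carry-over that differs between devices is not addressed by this change and should be acknowledged as a limitation.

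### The second device's off-mask baseline may be read as little as 5 minutes after the first device's highest-pressure step, with no recovery check, no named reference baseline and no period term

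*Combined protocol and SAP*

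**What the plan says.** Sections 4.2 and 4.6 describe a two-device, within-subject, single-session crossover. Section 3.1: "Twenty adult healthy volunteers will be recruited for this study". Section 4.2: "The decision of which device to begin with will be determined by random allocation of a coin toss".

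Each device run has four steps (4.6.1): an off-mask baseline, PS 0/PEEP 5, PS 5/PEEP 5, and PS 5/PEEP 10 cm H2O. On the first step the text is "A baseline will be established breathing without the NPPV mask attached". Timing is in 4.6.2: "Each step will consist of a 5-minute stabilization period, and then readings will be taken over the next two minutes". The change of device is in 4.6.3: "Following all four steps with the initial device, the second device will be applied and steps 1-4 repeated".

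Section 5.0 names a two-way ANOVA for the device influence and says that "initial comparisons will be made using paired" t-tests against baseline. It does not say whether that means each run's own baseline or the first one. Time is mentioned only in a conditional multivariate ANOVA, where it is not defined as period or order.

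On session length, section 6.0 says "The total procedure should be completed within 90-120 minutes".

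**The concern.** The two baselines share a label but are not the same condition. One precedes all pressure exposure; the other always follows the highest setting in the sequence. Between on-mask steps PEEP or pressure support rises by 5 cm H2O at most. Between runs PEEP 10 and PS 5 are removed together, and this larger change gets the same 5 minutes.

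The study expects pressure to alter end-expiratory lung volume and the distribution of ventilation (sections 1.0 and 2.0). Section 6.0 adds: "Although hyperventilation (i.e. lightheadedness, tingling in the hands) may occur as airway pressure is applied". Some residue after mask removal is therefore plausible, though nothing in the documents shows that it occurs.

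The comparisons with baseline in 5.0 are at stake. Change in EELI (4.8.2) depends most directly on the reference reading. Global tidal variation, the primary outcome (4.7), is exposed through the same paired tests.

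**Working it through.** The plan has no figure of its own to reproduce: no recovery time, SD, effect size, alpha or power is given.

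**1. Timing, from 4.6.2, 4.6.3 and 6.0.** Scheduled steps take 2 devices x 4 steps x (5 + 2) min = 56 min. Measured from removal of the first mask, with no added delay, the second baseline is read over minutes 5-7. The second run's on-mask steps 2, 3 and 4 are read over minutes 12-14, 19-21 and 26-28. A session of 90-120 min leaves 34-64 min unassigned, none of it designated as rest between devices. Five minutes is thus the specified minimum and not a known actual gap.

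**2. Illustrative residue.** Assume that the PEEP 10 effect E decays exponentially with time constant tau, keeps its direction, and adds to later readings. Tau is not in the documents; 2, 5 and 10 min are shown as a range. The mean residue over minutes a to b, as a share of E, is r = tau x (exp(-a/tau) - exp(-b/tau)) / (b - a).

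| Reading | tau 2 | tau 5 | tau 10 |
|---|---|---|---|
| Second baseline, min 5-7 | 5.2% | 30.3% | 55.0% |
| Run 2 step 2, min 12-14 | 0.2% | 7.5% | 27.3% |
| Run 2 step 3, min 19-21 | <0.1% | 1.8% | 13.6% |
| Run 2 step 4, min 26-28 | <0.1% | 0.5% | 6.7% |
| Second baseline if read at min 15-17 | <0.1% | 4.1% | 20.2% |

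**3. Change from baseline.**
- *Run-specific baseline.* Second-run changes are understated by r(baseline) - r(step). At step 4 this is about 5%, 30% (30.3 - 0.5) or 48% (55.0 - 6.7) of E. Averaged over both runs it is half of that.
- *First baseline throughout.* That bias does not arise. The on-mask residue stays in the second-run readings: up to 7.5% of E at tau 5 and 27.3% at tau 10, both at step 2, and less at later steps.

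Random order does not help in the first case. If only the second baseline is shifted by c, each device's mean change is biased by c/2 in size even at a 10:10 split.

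**4. Device contrast.** Let D be the difference between the devices' PEEP 10 effects, with a 10:10 split.
- *Raw on-mask values.* The contrast is pulled toward zero by r(step)/2 as a share of D. At steps 2, 3 and 4 this is 0.1% or less at tau 2; 3.7%, 0.9% and 0.2% at tau 5; and 13.7%, 6.8% and 3.4% at tau 10.
- *Change from own-run baseline.* The sign reverses. The contrast moves away from zero by (r(baseline) - r(step))/2, which at step 4 is about 2.6%, 15% or 24% of D.
- *Devices with the same effect (D = 0).* Neither bias arises.

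**5. Order and period.** With 20 coin tosses, P(exactly 10:10) = 17.6%, P(13:7 or worse) = 26.3% and P(14:6 or worse) = 11.5%. A shift c common to all second runs biases the device contrast by c x (difference in sequence sizes)/20. That is 0.3c at 13:7, 0.4c at 14:6 and 0 at 10:10. Balance alone does not settle the matter, because an unmodelled shift also adds to the error. Assume two-sided alpha 0.05 and 80% power without a shift. At 10:10, a shift of 0.25, 0.5 or 1.0 SD of the within-subject device difference then cuts power to 77%, 70% or 50% if period is omitted. With a period term it stays near 80%.

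**The case against.** The strongest reply is that the size of any residue is entirely assumed. Section 6.0 speaks of hyperventilation while pressure is applied, says nothing of persistence, and calls the pressures relatively low. Sections 1.0 and 2.0 concern effects under pressure, not after it is removed. If tau were 5-10 min, 5 minutes would also be too short for the on-mask steps in both runs, which is a wider problem. All of this stands, and carry-over could be negligible in healthy volunteers. The difference is that incomplete settling of the on-mask steps follows the same schedule in both runs, whereas the two baselines have different histories.

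The plan also has some protection. Order is randomized, an off-mask baseline is re-measured, and the second device's first on-mask reading comes at least 12 minutes after the first mask is removed. It would be wrong to say that there is no interval at all. The re-measured baseline also supplies the data for a recovery check; what is missing is the planned comparison.

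A reader might infer that carry-over pushes the trial toward its own hypothesis of no device difference. The documents do not support that. The pull on raw values is small over most of the range, it reverses on change from own-run baseline, and 5.0 does not say which form is used. For the same reason it cannot be stated as fact that second-run changes will be understated: that needs run-specific baselines and a real residue.

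**Conclusion.** The gap is real and modest. As written, the second baseline may be read 5 minutes after the highest-pressure step, nothing checks recovery, and the analysis fixes neither the reference baseline nor a period term. If a residue exists, the comparisons with baseline are the most exposed: about 5% to 55% of the PEEP 10 effect would sit in the second baseline for tau from 2 to 10 min. The raw device contrast is exposed to 14% of the device difference at most over the same range. These figures rest on an assumed exponential decay and an assumed range for tau; the true size is unknown. The case for acting is that the remedy is cheap and the needed readings are already scheduled.

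**What to change.** 1. **Section 4.6.3.** State a minimum off-mask interval between devices that is longer than the generic 5 minutes, and record the actual interval for each subject. About 15 minutes before the second baseline reading is an illustrative value. It would still leave about 20% of the effect at tau 10, so the check in item 2 matters more than the exact number.
2. **Section 5.0, baseline.** Say which baseline is the reference. Report second minus first baseline, by first device, for global tidal variation, EELI and the EIT monitor's Tidal Rate. The pneumotachometer sits at the mask (4.9.1), so it cannot supply the off-mask rate. Judge the difference against a pre-set tolerance on the mean shift; a breath-to-breath range is wide enough to pass a real shift. Repeat the step-versus-baseline and device comparisons without subjects outside the tolerance. With about 10 subjects per order, the split by first device is descriptive.
3. **Section 5.0, model.** Include period (order) in the within-subject device analysis.

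**Cost.** A short amendment, no new equipment or subjects, and about 10 more minutes supine per subject. Scheduled steps plus the added rest come to 56 + 10 = 66 min. This must be checked against the 90-120 minute session once belt placement, calibration, device change and the body positions in 4.9.3 are counted. If all steps on both devices were repeated in three positions, the steps alone would take 3 x 56 = 168 min.
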